6.2 Trial Flow Chart - Patients Randomized to No Treatment Control Group

| Trial Period: | Screening | Randomization ^a | SOC Tumor Resection | Post-Operative Follow-up |
|--|----------------|----------------------------|-------------------------|--------------------------|
| Week | -2 | -2 | 1 | 6 ^b |
| Scheduling window (days) | ±14 | ±14 | ±14 | -5/+7 |
| Administrative Procedures | | | | |
| Informed Consent ^c | X | | | |
| Informed Consent for Future Biomedical Research ^d | X | | | |
| Inclusion/Exclusion Criteria | X | | | |
| Subject Identification Card | X | | | |
| Medical History | X | | | |
| ECOG Performance Scale Assessment | X | | | |
| Concomitant Medication Review ^e | X | | X | X |
| Clinic Procedures/Assessments | | | | |
| Full Physical Examination ^f | X | | | |
| Directed Physical Examination ^f | | | X ^g | X |
| Vital Signs, Weight and Height ^h | X | | X ^g | X |
| 12-Lead Electrocardiogram (performed locally) | X ⁱ | | As clinically indicated | |
| SOC Tumor Resection | | | X | |
| Tumor Core Needle Biopsy ^j | | | X ^j | |
| Adverse Events Monitoring ^k | X | | X | X |
| Assessment of Surgical Complications | | | | X ^l |
| Laboratory Procedures/Assessments | | | | |
| Pregnancy Test- Urine or Serum β-HCG or FSH ^m | X ⁱ | | | X |
| PT/INR and aPTT | X ⁱ | | X ^{n,o} | X |
| CBC with Differential | X ⁱ | | X ⁿ | X |
| Chemistry | X ⁱ | | X ⁿ | X |
| Urinalysis | X ⁱ | | | |
| T3, FT4, and TSH | X ⁱ | | | |
| Blood for HLA typing | | | X ^{n,p} | |
| HIV/Hepatitis Screen | X ⁱ | | | |

| Trial Period: | | Screening | Randomization^a | SOC Tumor Resection | Post-Operative Follow-up |
|--|--|------------------|----------------------------------|----------------------------|---------------------------------|
| | Week | -2 | -2 | 1 | 6 ^b |
| | Scheduling window (days) | ±14 | ±14 | ±14 | -5/+7 |
| Protocol-Specific Specimen Collection | | | | | |
| Tissue Collection | Fresh tumor tissue for shipping (TIL analysis, histoculture, tumor cell isolation and IMR expression analysis) | | | X | |
| | Tumor tissue for FFPE (IHC; DNA for mutational analysis, TCR utilization, promoter methylation analysis; RNA for gene expression and miRNA analysis) | | | X ^{q,r} | |
| | Fresh tumor tissue for snap freezing (DNA isolation, metabolic profiling, laser capture microdissection) | | | X | |
| | Fresh non-malignant kidney tissue from resected tumor specimen for snap freezing (DNA isolation) | | | X | |
| | Fresh tumor tissue in RNAlater solution (RNA extraction, gene expression) | | | X | |
| | Fresh non-malignant kidney tissue in RNAlater solution (RNA extraction, gene expression) | | | X | |
| Blood | PBMC Phenotypic Analysis | | | X ^m | X |
| | PBMC Isolation and Cryopreservation (Antigen-specific T cell response evaluation) | | | X ^m | X |
| | Plasma (miRNA, and exosome evaluation) | | | X ^m | X |
| | Serum (biomarkers) | | | X ^m | X |
| | Blood for RNA isolation (gene expression, miRNA expression) | | | X ^m | X |
| | Blood for DNA isolation (TCR utilization) ^s | | | X ^m | X |
| Urine for exosome isolation and analysis | | | | X ^t | X |

- a. Randomization, initially 2:1 neoadjuvant MK-3475:controls. Randomization will occur only after written consent is obtained and will occur after all screening assessments have been completed.
- b. This follow up visit must occur no less than 30 days after the day of SOC tumor resection.
- c. Written consent must be obtained prior to performing any protocol-specific procedure. Results of a test performed prior to the subject signing consent as part of routine clinical management are acceptable in lieu of a screening test if performed within 28 days prior to screening.
- d. If the subject signs the FBR consent, leftover samples may be kept for Future Biomedical Research.
- e. Prior medications – Record all medications taken within 28 days of screening visit. Concomitant medications – Enter new medications started during the trial through the Safety Follow-up visit. Record all medications taken for SAEs as defined in Section 7.2
- f. Full PE at screening visit; Directed PE for all other visits.
- g. These procedures may be performed up to 36 hours prior to the start of the SOC RCC tumor resection surgical procedure.
- h. Vital signs include temperature, pulse, respiratory rate, weight and blood pressure. Height will be measured at screening visit only. Vital signs will be collected at screening, prior to the administration of each dose of trial treatment, at SOC tumor resection, and at post-operative follow-up.
- i. Laboratory tests for screening are to be performed prior to randomization. See section 7.1.3 for details regarding laboratory testing.
- j. During the surgical procedure and prior to cross-clamping of the renal artery, under direct vision a core needle biopsy of the RCC may be performed at the discretion of the operating surgeon and subject to local IRB approval.
- k. AEs and laboratory safety measurements will be graded per NCI CTCAE version 4.0. All AEs, whether gradable by CTCAE or not, will also be evaluated for seriousness.
- l. At this visit, the occurrence of any surgical complications within 30 days of the operative procedure will specifically be assessed.
- m. For female subjects of reproductive potential, a serum pregnancy test performed by the local study site laboratory will be required. Pregnancy tests (serum and/or urine tests) should be repeated if required by local guidelines. For women thought to be post-menopausal, serum FSH will be measured to confirm post-menopausal status.
- n. Blood for study related analyses may be collected at any time prior to surgery on the day of surgery. Ideally these blood samples will be collected via the iv cannula placed in preparation for surgery, but these samples may also be collected via venipuncture earlier on the day of surgery, at the discretion of the clinical care team.
- o. Blood for assessment of these coagulation parameters may be drawn up to 72 hours before the day of SOC tumor resection, at the discretion of the operative team. If such a sample is collected, a sample for these tests will not need to be collected on the day of surgery.
- p. Low resolution HLA-A and B typing, to be performed by local HLA typing laboratory.
- q. A minimum of 3 18-gauge core biopsy tumor samples may be collected intraoperatively under direct vision by the surgeon prior to cross-clamping of the renal artery on the side of the RCC (see footnote h). The harvested cores will be placed in single cassette for formalin fixation and paraffin embedding. The FFPE block will then be shipped to Central Laboratory for further processing and analysis.
- r. Following tumor resection, additional tumor tissue will be collected for formalin fixation and paraffin embedding. These FFPE blocks will then be shipped to Central Laboratory.
- s. Any leftover extracted DNA will be stored for future biomedical research if the subject signs the FBR consent.
- t. Urine will be collected prior to surgery on the day of the surgical RCC resection.

6.3 Trial Flow Chart - Patients Randomized to Neoadjuvant MK-3475 (3 DOSE REGIMEN)

| Trial Period: | Screening | Randomization ^a | Pretreatment Core Biopsy | MK-3475 | | | SOC Tumor Resection | Post-Operative Follow-up |
|--|----------------|----------------------------|--------------------------|-------------------------|----|----|---------------------|--------------------------|
| Week: | -2 | -2 | -1 | 1 | 4 | 7 | 10 | 15 ^b |
| Scheduling window (days) | ±14 | ±14 | ±6 | ±3 | ±3 | ±3 | -7/+14 | -5/+7 |
| Administrative Procedures | | | | | | | | |
| Informed Consent ^c | X | | | | | | | |
| Informed Consent for Future Biomedical Research ^d | X | | | | | | | |
| Inclusion/Exclusion Criteria | X | | | | | | | |
| Subject Identification Card | X | | | | | | | |
| Medical History | X | | | | | | | |
| ECOG Performance Scale Assessment | X | | | | | | | |
| Concomitant Medication Review ^e | X | | X | X | X | X | X | X |
| Clinic Procedures/Assessments | | | | | | | | |
| Full Physical Examination ^f | X | | | X | X | X | | |
| Directed Physical Examination ^f | | | | | | | X ^g | X |
| Vital Signs, Weight and Height ^h | X | | | X | X | X | X ^g | X |
| 12-Lead Electrocardiogram (performed locally) | X ⁱ | | | as clinically indicated | | | | |
| Tumor Core Needle Biopsy ^j | | | X ^k | | | | X ^l | |
| MK-3475 Administration ^m | | | | X | X | X | | |
| SOC Tumor Resection | | | | | | | X | |
| Adverse Events Monitoring ⁿ | X | | X | X | X | X | X | X |
| Assessment of Surgical Complications | | | | | | | | X ^o |
| Laboratory Procedures/Assessments | | | | | | | | |
| Pregnancy Test- Urine or Serum β-HCG or FSH ^p | X ⁱ | | | X | | | | |
| PT/INR and aPTT | X ⁱ | | | | | | X ^{q,r} | X |
| CBC with Differential | X ⁱ | | | X | X | X | X ^q | X |
| Chemistry | X ⁱ | | | X | X | X | X ^q | X |
| Urinalysis | X ⁱ | | | | | | | |
| T3, FT4, and TSH | X ⁱ | | | | X | | | X |
| Blood for HLA typing | | | X ^{s,t} | | | | | |
| HIV/Hepatitis Screen | X ⁱ | | | | | | | |

| Trial Period: | | Screening | Randomization ^a | Pretreatment Core Biopsy | MK-3475 | | | SOC Tumor Resection | Post-Operative Follow-up |
|--|--|-----------|----------------------------|--------------------------|----------------|----------------|----|---------------------|--------------------------|
| Week: | | -2 | -2 | -1 | 1 | 4 | 7 | 10 | 15 ^b |
| Scheduling window (days) | | ±14 | ±14 | ±6 | ±3 | ±3 | ±3 | -7/+14 | -5/+7 |
| Protocol-Specific Specimen Collection | | | | | | | | | |
| Tissue Collection | Fresh tumor tissue for shipping (TIL analysis, histoculture, tumor cell isolation and IMR expression analysis) | | | | | | | X | |
| | Tumor tissue for FFPE (IHC; DNA for mutational analysis, TCR utilization, promoter methylation analysis; RNA for gene expression and miRNA analysis) | | | X ^u | | | | X ^{v,w} | |
| | Fresh tumor tissue for snap freezing (DNA isolation, metabolic profiling, laser capture microdissection) | | | | | | | X | |
| | Fresh non-malignant kidney tissue from resected tumor specimen for snap freezing (DNA isolation) | | | | | | | X | |
| | Fresh tumor tissue in RNAlater solution (RNA extraction, gene expression) | | | | | | | X | |
| | Fresh non-malignant kidney tissue in RNAlater solution (RNA extraction, gene expression) | | | | | | | X | |
| Blood | PBMC Phenotypic Analysis | | | X ^t | | | | X ^q | X |
| | PBMC Isolation and Cryopreservation (Antigen-specific T cell response evaluation) | | | X ^t | | | | X ^q | X |
| | Plasma (miRNA, and exosome evaluation) | | | X ^t | | | | X ^q | X |
| | Serum (biomarkers) | | | X ^t | | | | X ^q | X |
| | Serum (PK/PD) | | | | X ^x | X ^y | | X ^q | X |
| | RNA isolation (gene expression, miRNA expression) | | | X ^t | | | | X ^q | X |
| | DNA isolation (TCR utilization) ^z | | | X ^t | | | | X ^q | X |
| Urine for exosome isolation and analysis | | | | X ^t | | | | X ^{aa} | X |

- a. Randomization, initially 2:1 neoadjuvant MK-3475:controls. Randomization will occur only after written consent is obtained and will occur after all screening assessments have been completed. Randomization can occur at any time point after screening and prior to core biopsy.
- b. This follow up visit must occur no less than 30 days after the day of SOC tumor resection.
- c. Written consent must be obtained prior to performing any protocol-specific procedure. Results of a test performed prior to the subject signing consent as part of routine clinical management are acceptable in lieu of a screening test if performed within 28 days prior to screening.
- d. If the subject signs the FBR consent, leftover samples may be kept for Future Biomedical Research.
- e. Prior medications – Record all medications taken within 28 days of screening visit. Concomitant medications – Enter new medications started during the trial through 30 days after the last dose of trial treatment. Record all medications taken for SAEs as defined in Section 7.2
- f. Full PE at screening and neoadjuvant MK-3475 treatment visits; Direct PE for all other visits.
- g. These procedures may be performed up to 36 hours prior to the start of the SOC RCC tumor resection surgical procedure.
- h. Vital signs include temperature, pulse, respiratory rate, weight and blood pressure. Height will be measured at screening visit only. Vital signs will be collected at screening, prior to the administration of each dose of trial treatment, at SOC tumor resection, and at post-operative follow-up.
- i. Laboratory tests for screening are to be performed within 28 days prior to the first dose of trial treatment. See section 7.1.3 for details regarding laboratory testing.
- j. If a diagnostic biopsy has already been performed per local SOC and sufficient tissue from that sample is available and will be submitted for all study-related analyses specified for the preoperative biopsy tissue, the study-specified pretreatment biopsy will not be required, and these assessments should be performed on the day that pretreatment blood and urine samples (see footnote w below) are collected.
- k. Percutaneous core needle biopsy of RCC performed under image guidance. This procedure may take place any time between randomization to the MK-3475 treatment group and the start of treatment with MK-3475. This study-prescribed pretreatment core needle biopsy is not required if a diagnostic biopsy has been performed per local SOC for diagnostic purposes, this biopsy will have been performed within 45 days prior to the first dose of MK-3475, and sufficient tissue is available from such a specimen for all study-related analyses specified for the pretreatment biopsy.
- l. During the surgical procedure and prior to cross-clamping of the renal artery, under direct vision a core needle biopsy of the RCC may be performed at the discretion of the operating surgeon and subject to local IRB approval.
- m. The number of doses of MK-3475 may be increased to three doses, based on the results of the first interim analysis, as described in Section 8.0 (See Table 9 for the flow chart should this occur).
- n. AEs and laboratory safety measurements will be graded per NCI CTCAE version 4.0. All AEs, whether gradable by CTCAE or not, will also be evaluated for seriousness.
- o. At this visit, the occurrence of any surgical complications within 30 days of the operative procedure will specifically be assessed.
- p. For female subjects of reproductive potential, a urine pregnancy test should be performed within 72 hours of the first dose of trial treatment. If urine pregnancy results cannot be confirmed as negative, a serum pregnancy test performed by the local study site laboratory will be required. Pregnancy tests (serum and/or urine tests) should be repeated if required by local guidelines. For women thought to be post-menopausal, serum FSH will be measured to confirm post-menopausal status.
- q. Blood for study related analyses may be collected at any time prior to surgery on the day of surgery. Ideally these blood samples will be collected via the iv cannula placed in preparation for surgery, but these samples may also be collected via venipuncture earlier on the day of surgery, at the discretion of the clinical care team.
- r. Blood for assessment of these coagulation parameters may be drawn up to 72 hours before the day of SOC tumor resection, at the discretion of the operative team. If such a sample is collected, a sample for these tests will not need to be collected on the day of surgery.
- s. Low resolution HLA-A and B typing, to be performed by local HLA typing laboratory.
- t. Blood and urine samples should be collected on the day of the pretreatment core biopsy. However, if tissue from a biopsy previously performed per local SOC for diagnostic purposes will be submitted for all specified study-related analyses, these blood and urine samples should be collected as close to the time of this biopsy as possible and must be collected prior to the first dose of MK-3475.

- u. A minimum of 3 18-gauge core biopsy tumor samples will be collected. The harvested cores will be placed in single cassette for formalin fixation and paraffin embedding. The entire specimen will then be cut onto slides. After the diagnosis of RCC is confirmed by the local site pathologist, the remaining tissue sections will be used for study related analyses.
- v. A minimum of 3 18-gauge core biopsy tumor samples may be collected intraoperatively under direct vision by the surgeon prior to cross-clamping of the renal artery on the side of the RCC. The harvested cores will be placed in single cassette for formalin fixation and paraffin embedding. The FFPE block will then be shipped to Central Laboratory.
- w. Following tumor resection, additional tumor tissue will be collected for formalin fixation and paraffin embedding. These FFPE blocks will then be shipped to Central Laboratory.
- x. Blood sample to be collected 30 minutes after the completion of MK-3475 dosing.
- y. Blood samples to be collected immediately prior to and 30 minutes after the completion of MK-3475 dosing.
- z. Any leftover extracted DNA will be stored for future biomedical research if the subject signs the FBR consent.
- aa. Urine will be collected prior to surgery on the day of the surgical RCC resection.

6.4 Trial Flow Chart – Post-Resection MK-3475 Treatment (All Subjects)

| Treatment Period: | Post-Resection MK-3475 (3-Week Cycles) | | | | End of Treatment or Discontinuation Visit ^c | Post-Treatment | |
|---|---|---|-----|------------------|--|------------------|-------------------|
| | 1 ^a | 4 | 7 | Q3W ^b | | 30 Day Follow-up | 90 Day Phone Call |
| Scheduling Window (days): | +3 | ± 3 | ± 3 | ± 3 | ± 3 | (±3) | (+7) |
| Clinical Procedures/Assessments | | | | | | | |
| MK-3475 Administration | X | X | | X | X | | |
| Adverse Events Monitoring ^d | X | X | | X | X | X | X |
| Concomitant Medication Review | X | X | | X | X | X | X |
| Laboratory Procedures/Assessments | | | | | | | |
| Pregnancy Test-Urine β-HCG | X ^e | | | | | X | |
| T3, FT4, and TSH | X | | X | X ^f | X | | |
| Laboratory Studies | Laboratory studies should be performed at the discretion of the treating physician. | | | | | | |
| PBMC Isolation and Cryopreservation (Antigen-specific T cell response evaluation) | | | X | | | | |
| Efficacy Measurements | | | | | | | |
| Tumor imaging | X ^g | Additional tumor imaging at the discretion of the treating physician ^h | | | | | |

- a. Post-resection MK-3475 administration should begin within 45 days (±15 days) following surgical RCC resection, but only after the Post-operative Follow-Up visit in Table 6.1, 6.2, or 6.3, and the subject has fully recovered from the surgical procedure.
- b. MK-3475 200 mg IV Q3W can be continued for up to 17 treatment cycles (1 year of treatment).
- c. If the Discontinuation visit occurs approximately 30 days from last dose of treatment, the same procedures do not need to be repeated for the 30 Day Follow-up visit.
- d. Record all AEs occurring within 30 days after the last dose of MK-3475. Report all SAEs (related and unrelated to trial treatment) and ECIs occurring up until 90 days after the last dose of MK-3475 or the start of new anti-cancer treatment, whichever comes first.
- e. For female subjects of reproductive potential, a urine pregnancy test should be performed within 72 hours prior to the first dose of trial treatment. If urine pregnancy results cannot be confirmed as negative, a serum pregnancy test performed by the local study site laboratory will be required. Pregnancy tests (serum and/or urine tests) should be repeated if required by local guidelines.
- f. Thyroid function testing (T3, FT4, and TSH) should be repeated every 6 weeks/every other cycle during post-resection treatment with MK-3475.
- g. Optional tumor imaging should ideally be performed prior to the start of post-resection MK-3475. For patients with known metastatic disease at the time of RCC resection, this imaging should be performed at least 30 days following surgery but before the first dose of post-resection MK-3475.
- h. The treating physician should obtain additional SOC tumor imaging studies as clinically indicated. For subjects with known metastatic disease at the time of RCC resection, local assessment of response should be assessed by the investigator using either RECIST v1.1 or irRECIST.

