For subjects without metastatic disease at the time of surgical RCC resection who experience drug-related toxicities above Grade 1 during neoadjuvant treatment, post-resection MK-3475 should also not be administered and the subject should be permanently discontinued. However, subjects with known metastatic disease at the time of surgical RCC resection who develop Grade 2 or greater drug-related AEs during neoadjuvant MK-3475 treatment may still be eligible to receive post-resection MK-3475 if the drug-related AE severity as listed in [Table 3](#) below does not prescribe permanent treatment discontinuation.

5.2.1.2.1.2 Post-Resection MK-3475

Post-resection administration of MK-3475 must be withheld for drug-related toxicities and severe or life-threatening AEs as per [Table 3](#) below. See Section 5.6.2 for supportive care guidelines, including use of corticosteroids to be followed during post-resection administration of MK-3475 (only applicable in the Post-Resection Phase of the study).

Table 3 Dose Modification and Toxicity Management Guidelines for Immune-related AEs Associated with Pembrolizumab (During Post-Resection Phase ONLY)

| General instructions: | | | | |
|------------------------------|---|--------------------------------------|---|--|
| Immune-related AEs | Toxicity grade or conditions (CTCAEv4.0) | Action taken to pembrolizumab | irAE management with corticosteroid and/or other therapies | Monitor and follow-up |
| Pneumonitis | Grade 2 | Withhold | 
 Administer corticosteroids (initial dose of 1-2 mg/kg prednisone or equivalent) followed by taper | 
 Monitor participants for signs and symptoms of pneumonitis Evaluate participants with suspected pneumonitis with radiographic imaging and initiate corticosteroid treatment Add prophylactic antibiotics for opportunistic infections |
| | Grade 3 or 4, or recurrent Grade 2 | Permanently discontinue | | |

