| Diarrhea / Colitis | Grade 2 or 3 | Withhold | 
 Administer corticosteroids (initial dose of 1-2 mg/kg prednisone or equivalent) followed by taper | 
 Monitor participants for signs and symptoms of enterocolitis (ie, diarrhea, abdominal pain, blood or mucus in stool with or without fever) and of bowel perforation (ie, peritoneal signs and ileus). Participants with \geq Grade 2 diarrhea suspecting colitis should consider GI consultation and performing endoscopy to rule out colitis. Participants with diarrhea/colitis should be advised to drink liberal quantities of clear fluids. If sufficient oral fluid intake is not feasible, fluid and electrolytes should be substituted via IV infusion. |
| | Grade 4 | Permanently discontinue | | |

| Immune-related AEs | Toxicity grade or conditions (CTCAEv4.0) | Action taken to pembrolizumab | irAE management with corticosteroid and/or other therapies | Monitor and follow-up |
|--|--|--|---|---|
| AST / ALT elevation or Increased bilirubin | Grade 2 | Withhold | 
 Administer corticosteroids (initial dose of 0.5- 1 mg/kg prednisone or equivalent) followed by taper | 
 Monitor with liver function tests (consider weekly or more frequently until liver enzyme value returned to baseline or is stable) |
| | Grade 3 or 4 | Permanently discontinue | 
 Administer corticosteroids (initial dose of 1-2 mg/kg prednisone or equivalent) followed by taper | |
| Type 1 diabetes mellitus (T1DM) or Hyperglycemia | Newly onset T1DM or Grade 3 or 4 hyperglycemia associated with evidence of β -cell failure | Withhold | 
 Initiate insulin replacement therapy for participants with T1DM Administer anti-hyperglycemic in participants with hyperglycemia | 
 Monitor participants for hyperglycemia or other signs and symptoms of diabetes. |
| Hypophysitis | Grade 2 | Withhold | 
 Administer corticosteroids and initiate hormonal replacements as clinically indicated. | 
 Monitor for signs and symptoms of hypophysitis (including hypopituitarism and adrenal insufficiency) |
| | Grade 3 or 4 | Withhold or permanently discontinue ¹ | | |

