| Hyperthyroidism | Grade 2 | Continue | 
 Treat with non-selective beta-blockers (eg, propranolol) or thionamides as appropriate | 
 Monitor for signs and symptoms of thyroid disorders. |
| | Grade 3 or 4 | Withhold or permanently discontinue ¹ | | |
| Hypothyroidism | Grade 2-4 | Continue | 
 Initiate thyroid replacement hormones (eg, levothyroxine or liothyronine) per standard of care | 
 Monitor for signs and symptoms of thyroid disorders. |
| Nephritis and Renal dysfunction | Grade 2 | Withhold | 
 Administer corticosteroids (prednisone 1-2 mg/kg or equivalent) followed by taper. | 
 Monitor changes of renal function |
| | Grade 3 or 4 | Permanently discontinue | | |

| Immune-related AEs | Toxicity grade or conditions (CTCAEv4.0) | Action taken to pembrolizumab | irAE management with corticosteroid and/or other therapies | Monitor and follow-up |
|--|---|---|---|--|
| Myocarditis | Grade 1 or 2 | Withhold | 
 Based on severity of AE administer corticosteroids | 
 Ensure adequate evaluation to confirm etiology and/or exclude other causes |
| | Grade 3 or 4 | Permanently discontinue | | |
| All other immune-related AEs | Intolerable/persistent Grade 2 | Withhold | 
 Based on type and severity of AE administer corticosteroids | 
 Ensure adequate evaluation to confirm etiology and/or exclude other causes |
| | Grade 3 | Withhold or discontinue based on the type of event. Events that require discontinuation include and not limited to: Guillain-Barre Syndrome, encephalitis | | |
| | Grade 4 or recurrent Grade 3 | Permanently discontinue | | |
| 
1. Withhold or permanently discontinue pembrolizumab is at the discretion of the investigator or treating physician.
 
NOTE: For participants with Grade 3 or 4 immune-related endocrinopathy where withhold of pembrolizumab is required, pembrolizumab may be resumed when AE resolves to \leq Grade 2 and is controlled with hormonal replacement therapy or achieved metabolic control (in case of T1DM).
 | | | | |

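### Table 3 makes stopping post-resection MK-3475 mandatory for attributed liver and renal events, but flow chart 6.4 mandates no chemistry test across up to 17 doses

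*Combined protocol and SAP*

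**What the plan says.** The duty to act is firm. Section 5.2.1.2.1.2 states: "Post-resection administration of MK-3475 must be withheld for drug-related toxicities and severe or life-threatening AEs as per" Table 3. Section 5.6.2 adds that the guidance applies when the investigator judges the event related to pembrolizumab, and need not be followed otherwise.

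The duty to measure is not firm. For the post-resection phase, flow chart 6.4 says: "Laboratory studies should be performed at the discretion of the treating physician". The exceptions are the pregnancy test, one PBMC sample for research, and thyroid function. On thyroid function, footnote f says: "Thyroid function testing (T3, FT4, and TSH) should be repeated every 6 weeks/every other cycle".

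Table 3 has monitoring text of its own:
- Liver: "Monitor with liver function tests (consider weekly or more frequently until liver enzyme value returned to baseline or is stable".
- Glucose: "Monitor participants for hyperglycemia or other signs and symptoms of diabetes".
- Renal: "Monitor changes of renal function".

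The last chemistry the protocol requires is at the post-operative visit. Footnote a of chart 6.4 lets post-resection dosing begin "but only after the Post-operative Follow-Up visit in Table 6.1, 6.2, or 6.3".

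**The concern.** A stopping rule protects subjects only if the quantity that triggers it is measured. Liver enzyme, bilirubin and creatinine changes can reach the action grades without symptoms. Adverse event review, which chart 6.4 does schedule, is poorly suited to finding them.

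The contrast with the neoadjuvant phase is marked. Charts 6.1 and 6.3 schedule chemistry at each of the two or three neoadjuvant doses. Chart 6.4 covers up to 17 doses and schedules none. Control subjects (3 to 12 of them under Table 4) meet MK-3475 for the first time in this phase.

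There is also a reporting consequence. Section 4.2.3.1 assesses safety in everyone who has received MK-3475, Section 8.2.2 lists laboratory assessments among the primary safety endpoints, and Section 8.2.3 defines the safety population as anyone given at least one dose. If testing depends on the physician, so does the detection of symptom-free laboratory abnormalities.

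**Working it through.** The plan states no figure to reproduce. The check compares texts and counts visits.

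**Rule against measurement**

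| Table 3 row | Action if attributed to pembrolizumab | Scheduled test in 6.4 |
|---|---|---|
| AST/ALT or bilirubin | Withhold at Grade 2; stop permanently at Grade 3-4 | None |
| Nephritis, renal dysfunction | Withhold at Grade 2; stop permanently at Grade 3-4 | None |
| New type 1 diabetes, or Grade 3-4 hyperglycemia with beta-cell failure | Withhold | None |
| Hypothyroidism | Row reads "Hypothyroidism | Grade 2-4 | Continue" | Thyroid tests, every other cycle |
| Hyperthyroidism | Continue at Grade 2; withhold or stop by judgment at Grade 3-4 | Thyroid tests, every other cycle |

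The scheduled test serves rows that mostly allow dosing to continue. The rows with a compulsory permanent stop at Grade 3-4 for liver and renal events have no scheduled test.

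**Does another section supply a minimum?**
- Section 5.2.2 requires the flow-chart assessments before dosing, so it adds nothing that 6.4 lacks.
- Section 7.1 allows extra safety tests but does not require them.
- Section 7.1.3.1 (Table 10) lists analytes without visits.
- Section 7.1.5.9 allows the timing of safety laboratory tests to be changed, and does not oblige anyone to test.
- Section 7.2.3.2 defines a hepatic event of clinical interest from scheduled or unscheduled results. In this phase no chemistry is scheduled.
- Table 3's liver interval runs until values settle, so it starts only after an abnormality is known. Its renal and glucose lines give no interval.

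Mandated chemistry panels from dose 1 onward: 0.

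**Longest interval the text allows**
- Dose 1 to dose 17, every 3 weeks: 16 × 21 = 336 days.
- Post-operative panel: day 30 to 42 after surgery (Section 7.1.5.5).
- Dose 1: day 45 ± 15, that is day 30 to 60, and not before that visit (6.4, footnote a). Panel to dose 1 is therefore 0 to 60 − 30 = 30 days.
- Panel to dose 17: 336 + 0 = 336 to 336 + 30 = 366 days. With nominal timing, (45 − 35) + 336 = 346 days.

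This excludes the ±3-day visit windows, interruptions, and later starts approved by the sponsor.

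**What the thyroid schedule would give**
- Draws at weeks 1, 7, 13, 19, 25, 31, 37, 43 and 49: 9, matching doses 1, 3, ..., 17. With end of treatment: 9 if that draw coincides with dose 17, otherwise 10.
- Doses without a same-visit panel: 17 − 9 = 8, each nominally 21 days after one, and at most 21 + 3 + 3 = 27 days.
- Blood at 6 mL per chemistry sample (Section 12.4): 9 × 6 = 54 mL to 10 × 6 = 60 mL.
- Panels if all 36 subjects complete: 9 × 36 = 324 to 10 × 36 = 360.

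These counts assume dosing at week 7 and every 3 weeks thereafter. As reproduced in the available text, chart 6.4 marks no week-7 dose and marks one at end of treatment, which is probably a shifted column.

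**The case against.** The strongest reply is that 6.4 delegates deliberately. Its row expects laboratory studies to be done and leaves the choice and timing to a physician whom Table 3 tells to watch renal function and glucose, and whom Section 5.2.1.2 reminds of the need for early recognition. Imaging is delegated in the same way. Nothing forbids chemistry at every cycle. All of that stands, but delegation without a floor means a site can follow the protocol exactly and give 17 doses with no chemistry.

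Three stronger readings are tempting, and the documents support none of them:
- **A grade alone forces a stop.** It does not. Section 5.6.2 ties the guidance to the investigator's attribution. A creatinine rise put down to the nephrectomy does not trigger the renal row, so recent surgery is not by itself an argument about that row. But attribution cannot begin until an abnormality has been seen.
- **Subjects will go about a year untested.** The documents do not say how often physicians test. The 336 to 366 days measure the missing rule, not expected practice.
- **The primary safety objective fails, or is wholly untouched.** Section 3.1 states that objective for neoadjuvant dosing, where chemistry is scheduled, and the laboratory summaries are descriptive. But Sections 4.2.3.1, 8.2.2 and 8.2.3 take in laboratory data from everyone dosed, so uneven ascertainment is possible. No power or sample-size figure changes.

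It can also be said that Section 7.1.5.9 already lets the sponsor adjust safety tests by letter. That route is optional, depends on new data, states that the number of procedures per subject will not rise, and caps extra blood at 50 mL. Finally, the Administrative Binder and Investigator Trial File Binder were not available and may contain monitoring advice. The finding concerns the protocol text.

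**Conclusion.** The gap is real and should be fixed. The protocol compels action on attributed liver and renal events but compels no chemistry that would reveal them: 0 mandated panels over up to 17 post-resection doses, and none at any time on drug for control subjects. The main consequence is for subject safety. A secondary one is that descriptive laboratory data from this phase may reflect how often each physician tested. How large either effect is in practice depends on discretionary testing, which the documents do not describe. The conclusion rests on the protocol text alone and on dosing every 3 weeks as scheduled.

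**What to change.** In flow chart 6.4, replace the discretion line with a minimum chemistry panel of AST, ALT, bilirubin, creatinine and glucose at the visits that already draw thyroid tests: week 1, week 7, every other cycle after that, and end of treatment. Require the results to be reviewed before dosing at those visits. Leave further tests, including those at the intervening doses, to the treating physician. The six-week interval is chosen because the draws already exist; the documents do not derive it, and the sponsor could reasonably choose a shorter one.

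The cost is about 54 to 60 mL of blood per subject completing 17 doses, at most 324 to 360 local panels (some probably already drawn as routine care), and local turnaround before infusion at up to 9 dosing visits. No visit is added. Chart 6.4 and the Section 12.4 volume tables need amending. The added volume exceeds the 50 mL discretionary allowance, so it must be written into those tables. They already leave out the post-resection thyroid draws, so their printed totals are incomplete and the increase should not be expressed as a percentage of them.
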